6.1.6 Study and Data Monitoring

During the course of the study, the PI and the DCC will work in conjunction with the DSMC to ensure that the trial is conducted properly and in accordance with the study protocol. Before study initiation, the DCC will organize the initial meeting of the DSMC to allow the committee members to review, offer advice, and approve the study protocol, informed consent form, and other supporting study documents. During this meeting, the overall plan for safety monitoring and procedures and guidelines for reporting adverse events will be reviewed and approved by the DSMC. In addition, the overall plan for statistical analysis and monitoring the study for early stopping and/or pausing enrollment will be discussed. Thereafter, the DSMC will meet on an approximate biannual basis. The DCC will produce data tables and conduct analyses as appropriate for review by the DSMC.

Protocol monitoring will be a continuous process performed both at the DCC and at the Enrollment Center. The DCC staff will be in regular communication with both Study Coordinators and the PI, via email or teleconference, at least monthly to discuss general study issues and to assure the site is up to date with data completion. At least monthly, data quality reviews will be conducted to assess level of missing data, review requests for missing values and missing forms exceptions, and run data checks for missing and inconsistent data. Any departure from procedures or requirements outlined in the protocol will be classified as protocol deviations. Prior to study initiation, a site initiation visit will be conducted by a DCC protocol monitor to ensure the site possesses adequate facilities and staffing to conduct the study, that site personnel have sufficient knowledge to ensure the study is conducted in accordance with GCP, applicable regulations, and the approved protocol, and that they are adequately trained in study policies and procedures. Interim monitoring visits will be conducted to monitor for informed consent documentation, protocol adherence, reporting of protocol deviations, study outcomes, participant safety, maintenance of appropriate source documentation and regulatory reviews. Protocol monitoring visits conducted by a DCC monitor will occur approximately every 6 months after enrollment begins. A site close-out visit will be conducted at the conclusion of the study. Complete and accurate regulatory documentation, complete data entry, and no pending action items are required before the site is closed out.

6.2 Rationale for Study Design

Human CD34+ cells in bone marrow are mobilized into the circulation in response to tissue ischemia and play an important role in tissue revascularization.^{4,22} By injecting the isolated CD34+ cells from bone marrow directly into the vitreous cavity, the regenerative potential of these cells may be maximized to treat retinal ischemia. Animal studies have shown that intravitreally injected human CD34+ cells home into sites of retinal injury and ischemia and may play a role in revascularization. This has been demonstrated in animal models of diabetic retinopathy, acute retinal ischemia-reperfusion injury and retinal laser injury,¹³⁻¹⁹ Thus, we hypothesize that these CD34+ cells may help cells in the retina recover from ischemia and regain visual function. RVO is the condition to be studied since it is the second most common retinal vascular cause of vision loss. With RVO the retinal ischemic event is usually acute, rather than chronic and progressive as noted in diabetic retinopathy, potentially allowing therapeutic effect of cellular therapy to be appreciated more readily. Since this is primarily an early phase safety and feasibility study, we will only enroll individuals with severe persistent vision loss from CRVO despite standard of care treatment with laser, surgery or intravitreal anti-vascular endothelial growth factor (VEGF) or corticosteroid therapy, if eligible (refer to Section 7.1.2 Inclusion/Exclusion Criteria). CRVO was selected to maintain uniformity in the study eye. It is of note that at least six participants with vision loss from various ischemic and degenerative retinal conditions have already been treated with this cellular therapy as part of a phase I study, and no safety or feasibility issues were noted during the 6 to 24 month follow-up.²³ Among the study eyes, the eye with vision loss from a combined CRVO and retinal artery occlusion appeared to have the greatest improvement by visual acuity, ERG, fluorescein angiography and microperimetry following this cellular therapy. The improvement was noted as early as one month following cell injection and sustained during the six-month follow-up period of the study. This proposed expanded phase I/II study is planned to further explore the effect of intravitreal autologous CD34+ cells in eyes with persistent vision loss from CRVO. By conducting a larger study of CRVO with longer follow-up, more feasibility and safety information can be obtained regarding this therapy. By comparing retinal functional and anatomic changes following study treatment to sham treatment, some efficacy information can also be obtained. Autologous CD34+ cells will be used to avoid cell rejection issues. These CD34+ cells will be harvested from bone marrow, one of the richest sources for these cells.¹⁻³ Although CD34+ cells mobilized into the circulation have been used for bone marrow transplantation, these mobilized cells may not completely share the characteristics of CD34+ cells in bone marrow.

The study is a randomized prospective study in which participants and all study personnel participating in eye examinations and outcome assessment will remain masked for the study duration of 12 months. Only the advanced retinal imaging team, treating ophthalmologist, the hematologist conducting bone marrow aspiration, and the study coordinator conducting these treatment and immediate post-treatment examination visits will be unmasked. All participants will remain masked for the study duration. The study design allows all participants to receive cellular therapy by month 6. The rationale for this study design is based on the expectation that participants receiving intravitreal cell injection would likely note a beneficial effect of cellular therapy, if any, by month 3 based on the observations of the preliminary phase I study.²²

The proposed clinical trial is supported by preclinical observations. Human CD34+ cells from bone marrow have been shown to be multi-potent and observed to home into ischemic retinal blood vessels and damaged retinal cells very quickly following intravitreal injection in animal models.¹⁵⁻¹⁹ These human cells could be detected in mouse retinal vasculature as long as 6 months following intravitreal injection in a murine model of acute retinal ischemia-reperfusion with apparent normalization of the retinal vasculature.¹⁷ No long-term safety issues were noted locally or systemically in the murine study. Of note, the number of CD34+ cells injected into the murine eyes in these preclinical safety studies is equivalent to about 10 million CD34+ cells injected in human eyes if adjusted for differences in eye size and volume. Thus, the upper limit of number of viable nucleated CD34+ cells to be injected intravitreal for this phase I/II study will be 10 million, where the cell count is based on the Miltenyi CliniMACS cell sorting process.

6.3 Outcome Measures

6.3.1 Primary Safety and Feasibility Outcome Measures

The primary outcome measures for the safety and feasibility of the stem cell therapy are the following:

- Incidence and severity of ocular and systemic adverse events reported during Study Period 1 (i.e., the day of the first treatment (Treatment 1) up to but not including the day of the second treatment (Treatment 2)
- The mean and range of number of CD34+ cells isolated from the bone marrow aspirate and the number injected into the eye

6.3.2 Secondary Outcome Measures

The secondary safety outcome measures are the incidence and severity of ocular and systemic adverse events reported throughout study duration.

The secondary efficacy outcome measures for the study will be used to describe the effect of therapy on retinal function and morphology as outlined in **TABLE 3**.

TABLE 3: Secondary Efficacy Outcome Measures							
Modality	Outcome Measure						
Visual Acuity	ETDRS Visual Acuity Letter Score						
	% Reduced Sensitivity						
Microperimetry	Average Threshold						
	Macular Thickness by ETDRS zone						
	Macular Volume						
	Average Macular Thickness						
	Presence of CME						
	Presence of Subretinal Fluid						
OCT	Integrity of Photoreceptor Layer (IS/OS Junction)						
	Integrity of Photoreceptor Layer (ELM)						
	Presence and number of hyper-reflective foci in vitreous, intraretinal and subretinal						
	Length of longest DRIL in line scans						
	Presence of ERM						
	Presence of VMT/VMA						
	Foveal avascular zone size						
	Automated Superficial and Deep Vascular Density (VD) by ETDRS zone						
0.074	VD Analysis of Superficial plexus and deep plexus						
OCTA	RNFL Thickness						
	Whole image capillary density %						
	Inside disc capillary density %						
	Retinal peripapillary capillary density %						
	Number of abnormal amplitude hexagons						
Multifocal ERG	Mean amplitude S.D.						
	Number of abnormal latency hexagons						
	Mean Latency S.D.						
	% normal amplitude for a-wave and b-wave under scotopic conditions						
	% normal latency for a-wave and b-wave under scotopic conditions						
	% normal amplitude for a-wave and b-wave under photopic conditions						
	% normal latency for a-wave and b-wave under photopic conditions						
Full-field ERG	% of normal Flicker amplitude and latency						
	% normal amplitude for Dark adapted 3.0 ERG + OP a-wave and b- wave under scotopic conditions						
	% normal latency of Dark adapted 3.0 ERG + OP a-wave and b-wave under scotopic conditions						
	Area of decreased autofluorescence						
Autonuorescence (AF)	Area of increased autofluorescence						

TABLE 3: Secondary Efficacy Outcome Measures						
Modality	Outcome Measure					
	Degree of retinal hemorrhages by ETDRS/Networc zones					
	Degree of pigment changes by ETDRS/Networc zones					
Fundus Photography	Degree of retinal fibrosis by ETDRS/Networc zones					
	Degree of NV by ETDRS/Networc zones					
	Degree of pre-retinal hemorrhage by ETDRS/Networc zones					
	Foveal avascular zone integrity					
	Area of non-perfusion within ETDRS Grid					
Fluerossein Angiegrem (FA)	Area of non-perfusion within Networc Grid					
Fluorescein Anglogram (FA)	Grade of capillary non-perfusion					
	Number of microaneurysms					
	Grade of telangiesctatic vascular changes					
Quality of Life	Mean total score					
	Mean subscale scores					

6.3.3 Exploratory Outcome Measures

Exploratory outcome measures include:

- Changes in the retina and retinal vasculature at a cellular level as visualized using Adaptive optics-OCT instrument in the study eye at 1 month following each treatment.
- Changes in the retinal vascular density and retinal morphology using ultrahigh resolution swept-source OCT and OCTA in the study eye at 1 month following each treatment.
- Characterization of the hematopoietic and endothelial stem cell subcomponents and subcomponent of cells with VEGFR-2 in the harvested CD34+ cell population.
- Number of participants who were able to correctly identify the timing of receipt of sham and cellular therapies.

6.4 Safety Plan

To ensure safety of participants and integrity of data in this trial, the following data and safety monitoring plan will be followed during the study:

1. The site investigators will continuously monitor participant safety and be responsible for reporting adverse events and serious adverse events (SAEs) from the Enrollment Center to the DCC Medical Monitor (MM) through Advantage eClinical, the electronic data capture system developed and maintained by the DCC. In order to maintain masking, the unmasked treating ophthalmologist will review any AE or SAE noted within 14 days following study treatments and determine severity and possible relationship to study treatment or procedure. He/she will report these adverse events to the Medical Monitor as noted above. Any AE or SAE noted later than 14 days after study treatments will be reviewed by the masked investigator (usually PI) who will review the events for severity and possible relationship to study therapy or procedure. The AE or SAE will be reported to the MM as noted above. To maintain masking as much as possible, for SAEs

determined by the MM to be related to study treatment and unexpected, the MM will share the SAE narrative with the PI. The reporting to the IRB of record will be done in a masked fashion as "Cellular Therapy/Sham Therapy". The investigator who originally reported the adverse event will be responsible for determining relationship to therapy and severity and following events through resolution.

- 2. The site Principal Investigator is required to review all unanticipated problems involving risk to participants or others, serious adverse events, and all participant deaths associated with the protocol and provide an unbiased written report of the event.
- 3. The DCC Medical Monitor will continuously monitor safety information provided by the site throughout the trial. All SAEs will be reviewed at the time they are reported. The DCC Medical Monitor will communicate the reporting of the SAE via email to the PI, the NEI Project Officer and the DSMC after review and confirmation of SAE has been completed. The Medical Monitor will also indicate whether he/she concurs with the details of the report provided by the site investigator. Reviews will be conducted in Advantage eClinical and will be a part of the safety database. All adverse events will be reviewed on a weekly basis to observe trends or unusual events. If any concerning safety patterns are noted, this information will be preserved as much as possible unless safety considerations dictate otherwise.
- 4. Data and Safety Monitoring Committee (DSMC): An independent DSMC will review participant data biannually, or on a schedule otherwise requested by the DSMC, to monitor for the occurrence of any unexpected risks or futility of treatment during the course of the study. The DSMC will convene and operate based on a pre-established charter created prior to the initiation of the trial. The DSMC will be permitted to seek additional independent expertise, as needed. The DSMC will provide safety oversight of the trial, monitor the progress of the study, and recommend continuation or modification of the trial, as appropriate. A summary of the review, including the recommendation to continue or modify the study, will be distributed to the site for submission to the local regulatory agencies.

This study will be conducted under an IND that has been cleared by the FDA because the study explores the safety of an experimental treatment for treating retinal disease. Thus, the study will comply with the adverse events definitions and reporting requirements for clinical trials established by the FDA and as outlined in Section 8.0 of the study protocol.

There were no observed adverse effects of intravitreal injection of human CD34+ cells from bone marrow in animal models.¹⁷ In addition, there were no systemic or ocular adverse events noted among the participants that have already been treated with intravitreal autologous CD34+ bone marrow stem cells under the cross-referenced IND for this study treatment.²³ Nonetheless, in order to minimize the risk of intraocular infection (i.e., endophthalmitis) or any other adverse effects that may be associated with intravitreal injection or cell therapy, the following precautions will be taken:

- The fluid obtained from washing the cells after CD34+ cell isolation will be cultured for 14 days.
- Gram stain and endotoxin measurement of the fluid obtained from washing the isolated cells will be performed stat and before the cells are released for intravitreal injection.

- The study eye will be cleansed with 5% betadine and sterile lid speculum will be used to open the eyelid before intravitreal injection is performed. Antibiotic drops will be used after the injection for one week.
- The injected participants will be examined one day, one week and one month after injection to look for evidence of endophthalmitis or other side effects of the injection. The 1 day and 1-week evaluation will be done by the unmasked treating ophthalmologist. The 1-month evaluation will be conducted by the masked ophthalmologist (usually PI). Intravitreal injection of drug is routinely done in the eye clinic under topical anesthesia with minimal risk of side effects from the injection. Endophthalmitis incidence has been reported to be < 1% per injection and usually diagnosed during the first week after injection.²⁹ Retinal tear and detachment, bleeding, cataract, and transient glaucoma are also potential side-effects of the injection but occur much less frequently. If these new conditions occur within 1 month of study procedure, they may be related to study treatment. Otherwise, it will be assumed unlikely to be related to study treatment. If any of these conditions occur, the participant will be promptly treated based on what is considered standard of care.
- Enrollment will be staggered by at least two weeks during the first 6 months of the enrollment period starting from the date the study is open to enrollment in case any adverse event associated with the study treatment is observed. Thereafter, enrollment may be slightly accelerated to maintain study timeline.

In addition, the following pause guidelines have been established. If any of the following events occur, enrollment will be paused, and the data reviewed by the DSMC.

- 1. Development of any new intraocular tumor in the injected eye during the study period in any participant.
- Endophthalmitis or Severe Inflammation resulting in > 3 lines of vision loss attributable to the study therapy in any participant, i.e., final culture of cell isolate shows organism despite negative immediate release tests, or this AE is noted in two or more participants despite negative final culture and immediate release tests.
- 3. Loss of vision of > 3 lines not attributed to normal progression of the eye condition, noted in two or more participants during the study period. The DSMC will be notified at the time that one participant has loss of vision of > 3 lines, but a pause would not be triggered until a second participant experiences the event.
- 4. New retinal vascular event in the study eye during the study period noted in two or more participants not attributable to normal progression of the underlying eye condition during the study period.
- Development of ocular neovascularization in the study eye not attributable to normal progression of the underlying eye condition during the study period in two or more participants.
- 6. Development of new sustained elevation in intraocular pressure above 30 mmHg not controlled with medical therapy and/or paracentesis and directly attributed to the studied therapy in any participant.

7. Any adverse event leading to enucleation or loss of the eye directly related to study therapy.

These guidelines may be further refined by the DSMC before initiation of the study. In the event any of these pause guidelines are triggered during the course of the study, both the IRB and FDA will be notified within 7 days and the study enrollment will be paused until further notice from the FDA and/or IRB. The study participant will be followed and treated according to standard of care until condition stabilizes or resolves.

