[#]Vital signs at Study Treatment 1 and Study Treatment 2 will be performed just before and after bone marrow or sham aspiration.

**For females of child-bearing potential (see APPENDIX B for definition), urine pregnancy testing should be done within 2 weeks prior to sham or cellular therapy.

[^]Using refraction previously obtained at Baseline visit.

[®]Study Treatment 1 and Study Treatment 2 eye examinations will be done before and after sham or cellular therapy.

***Includes full field and multifocal ERG.

^{@@} Includes research-grade ultra-high-resolution OCT and OCTA and adaptive optics-OCT in select patients who sign a separate consent. Advanced retinal imaging will be done on a separate day than the standard OCT/OCTA due to the time required for imaging. Imaging will be performed at baseline and participants with high quality images will have repeat imaging at 1 month after stem cell treatment, with at least 2 of the participants randomized to the deferred cellular therapy arm also having imaging after sham therapy. The images will be acquired and processed by unmasked investigators. Images will be masked prior to their review by a masked investigator and groups of images will be reviewed together to preserve masking.

^{##} For Immediate Cell Therapy/Deferred Sham Therapy group, study treatment at Day 0 consists of bone marrow aspiration followed by intravitreal injection of CD34+ cells, and study treatment at 6 months consists of sham bone marrow aspiration followed by sham injection. For Immediate Sham Therapy/Deferred Cell Therapy group, treatment at Day 0 consists of sham bone marrow aspiration followed by sham injection. For Immediate Sham Therapy/Deferred Cell Therapy group, treatment at Day 0 consists of sham bone marrow aspiration followed by sham injection, and study treatment at 6 months consists of bone marrow aspiration followed by intravitreal injection of CD34+ cells.

^{^^} The incorporation of the Exit Visit results from changes made to protocol v8.0 where follow-up was shortened to one year. For those participants who completed the Month 12 visit prior to the approval of protocol v8, they will complete the Exit Visit within 30 days of the approval of protocol v8.0. The Exit Visit is comprised of review and close-out of AEs and concomitant medication records, and completion of the study satisfaction survey.

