7.8.2 Analysis of Primary and Secondary Outcomes

7.8.2.1 Safety and Feasibility

Any ocular or systemic adverse events (AEs) from all participants will be utilized to summarize safety data for this phase I/II study. All reported AEs will be analyzed and subdivided into pretreatment and post-treatment AEs, where post-treatment is defined as those occurring on or after the day of the first treatment (cellular or sham). AEs will be summarized by presenting the number of events, and also by counts and frequencies for the number of participants with AEs, and the severity and relatedness of each AE to study treatment (i.e., CD34+ cells) or study procedure (i.e., intravitreal injection). Events related to bone marrow or sham aspiration will also be presented. Detailed listings of post-treatment AEs and pre-treatment AEs will be provided. All AEs will be coded using MedDRA[®] dictionary version 21.0 or higher. A similar approach will be taken to the presentation of Serious Adverse Events (SAEs).

Time trends in the occurrence of adverse events are also of interest. The primary safety outcome will be assessed at month 6 (at the end of Study Period 1). Adverse events that occur during the Study Period 1 will be broken down by whether the AE occurred following the sham or cellular treatment to assess differences in the adverse event experience between the two treatment arms. In addition, in order to assess whether there are any trends in when adverse events are reported from time of cellular therapy, we will also present adverse events based on how much time has elapsed from receipt of cellular therapy. Depending on how many events are reported, we may create categories for reporting purposes (e.g., events reported between Day 0 and 1-month post-therapy, events reported between 1 and 6 months, events reported between 6 and 12 months, etc.). In this analysis, data will be collapsed over both treatment arms.

To assess feasibility, the number and percent of study participants undergoing successful bone marrow aspiration will be summarized. The mean and range of volume of bone marrow aspirate, number of CD34+ cells isolated and number of CD34+ cells injected intravitreally will be described.

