8.1 Definitions

An adverse event (AE) is any untoward medical occurrence, whether or not considered treatmentor procedure-related, which occurs during the conduct of the study. Medical conditions or diseases present before a participant has study treatment on Day 0 are only considered adverse events if they worsen after the participant has signed ICF (temporal association).

A suspected adverse reaction is any adverse event for which there is a reasonable possibility that the study treatment caused the adverse event. A reasonable possibility implies that there is evidence that the study treatment caused the event.

An adverse reaction is any adverse event caused by the study treatment.

A Serious Adverse Event (SAE) is defined as any adverse event that suggests a significant hazard, contraindication, side effect, or precaution. This includes, but may not be limited to any of the following events:

- 1. Death
- 2. Life-threatening (Life-threatening means that the study participant was, in the opinion of the investigator, at immediate risk of death from the reaction as it occurred.)
- 3. Persistent or significant incapacity or substantial disruption of the ability to conduct normal life functions
- 4. Inpatient hospitalization or prolongation of existing hospitalization
- 5. Congenital abnormality or birth defect
- 6. Important medical event that may not result in one of the above outcomes, but may jeopardize the health of the study participant or require medical or surgical intervention to prevent one of the outcomes listed in the above definition of serious event
- 7. Vision-threatening (Refer to Section 8.3, Vision threatening Adverse Events)

Hospitalization or surgery for diagnostic or elective procedures for a preexisting condition is not considered an SAE. A pre-existing condition can be an SAE if the frequency, intensity or character of the condition worsens after signing of informed consent. If any questions arise regarding what may qualify as an adverse event or SAE, the Medical Monitor at the DCC will be consulted.

Unexpected Event or Reaction: An event or reaction is considered "unexpected" when its nature (specificity) or severity is not consistent with applicable product information, such as safety information provided in the package insert, the investigational plan, or the investigator's brochure.

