8.4 Causality

The Investigator will use the following question when assessing causality of any adverse event to study treatment: Is there a reasonable possibility that the administered cellular product caused the event? An affirmative answer designates the event as a suspected adverse reaction.

In addition, each adverse event will be assessed for its relationship to study procedures, including the injection itself. The Investigator will use the following question when assessing causality of an adverse event to study procedure: Is there a reasonable possibility that the intravitreal injection procedure caused the event?

The Medical Monitor at the DCC is available for consultation on assessing causality. For SAEs, the Medical Monitor will evaluate all reported SAEs against all accumulating knowledge regarding the study treatment. If the Medical Monitor's causality determination differs from the Investigator's assessment, the Medical Monitor's determination will prevail for regulatory reporting purposes.

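### Protocol 6.4 presumes that listed ocular events arising after 1 month are unlikely to be treatment-related, and this is not reconciled with the untimed, event-by-event causality assessment in 8.4

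*Protocol*

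**What the plan says.** In Protocol 6.4, the bullet on post-injection examinations lists retinal tears and detachments, bleeding, cataract and short-lived glaucoma as possible effects of the injection. Endophthalmitis is mentioned in the sentence just before. Two sentences on timing follow. The first is "If these new conditions occur within 1 month of study procedure, they may be related to study treatment". The second covers everything else: "Otherwise, it will be assumed unlikely to be related to study treatment".

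Three other places deal with relatedness and set no such limit.

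- Protocol 8.4 puts two questions to the investigator: "Is there a reasonable possibility that the administered cellular product caused the event" and, separately, "Is there a reasonable possibility that the intravitreal injection procedure caused the event". The first is to be used for any adverse event, the second for each one.
- Protocol 8.1, repeated in SAP 4.2.3, gives the matching definition: "A suspected adverse reaction is any adverse event for which there is a reasonable possibility that the study treatment caused the adverse event". It adds that such a possibility implies evidence of causation.
- Protocol 6.4, item 1, divides review by when an event is noted. The unmasked treating ophthalmologist takes events noted in the 14 days after study treatments. Later ones go to the masked investigator, "who will review the events for severity and possible relationship to study therapy or procedure". The unmasked reviewer has the same task.

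Relatedness is then tabulated under Protocol 7.8.2.1 and SAP 7.1.1.

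**The concern.** Section 6.4 settles by date a question that 8.4 leaves to judgement. An investigator faced with, say, a cataract first seen at the month 3 visit finds one instruction to presume the link unlikely and another to ask whether the cells, or the injection, could reasonably have caused it. Two investigators could follow the protocol faithfully and record different answers.

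The object of the presumption adds to the difficulty. The 6.4 bullet reasons from side effects of the injection, for which a short window is natural, but it applies the cut-off to study treatment. The analysis sections use that term for the CD34+ cells. The protocol's own rationale (4.0 and 6.2) reports that human cells were still detectable in mouse retinal vessels as long as 6 months after injection, so a 1-month limit for the product does not follow from the reasoning given for the needle.

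At stake is the relatedness classification in a trial whose primary objective is safety and feasibility. If the presumption is applied, late events of the listed types drift toward unrelated.

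**Working it through.** The plan gives no figure to reproduce, so the check sets the texts side by side.

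1. **Scope.** The 6.4 sentences cover the listed ocular conditions and arguably endophthalmitis, since the reference back to these conditions is loose. Section 8.4 covers any adverse event. The listed conditions therefore fall under both.

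2. **Time.** Section 6.4 sets 1 month from a study procedure. Sections 8.1 and 8.4 and SAP 4.2.3 set nothing. The 14-day split in 6.4, item 1, decides who reviews an event, not how relatedness is judged.

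3. **Form of the answer.** Section 8.4 asks a yes-or-no question, and a yes makes the event a suspected adverse reaction. Unlikely is not one of its answers, so the 6.4 presumption has no defined place in the record.

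4. **Object.** The Table 2 footnote says that for the immediate-cell group "study treatment at Day 0 consists of bone marrow aspiration followed by intravitreal injection of CD34+ cells". Protocol 7.8.2.1 speaks of "relatedness of each AE to study treatment (i.e., CD34+ cells) or study procedure (i.e., intravitreal injection"). In the first sense the presumption cuts across both 8.4 questions. In the second it cuts across the product question only and leaves the procedure question alone. Either way it meets at least one 8.4 question head-on.

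5. **Precedence.** Section 6.4 says that the study will follow the adverse event definitions and reporting requirements outlined in Section 8.0. That is a general pointer. It does not mention the 1-month sentences or say which text prevails. The SAP does not mention the presumption at all.

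6. **Reach (not a count of errors).** Table 2 has five post-treatment visits in each period: day 1, week 1 and months 1, 3 and 6. In Study Period 1 the earliest in-window month 3 visit is day 91 − 14 = 77, and the earliest month 6 visit is day 181 − 30 = 151. Both lie well past 28 to 30 days, so 2 of 5 visits fall wholly in the range where the presumption applies. The month 1 window runs from day 28 − 7 = 21 to day 28 + 7 = 35, so it straddles the limit, and 1 month is not defined in days.

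7. **What depends on relatedness.** The relatedness tables in Protocol 7.8.2.1 and SAP 7.1.1 do. Incidence, severity, the Period 1 comparison of all events between cell and sham, and the displays by time since therapy (including 6 to 12 months after cells) do not.

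**The case against.** The best reply is that the two texts can live together. The sentence sits in a list of precautions, in a bullet about follow-up visits, and its wording is graded. It does not call late events unrelated or exempt them from 8.4. Section 8.1 asks for evidence of causation, so a rebuttable default of unlikely comes close to what 8.1 would produce anyway. Section 6.4 also points to Section 8, and the section headed Causality is the natural operative text.

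Much of this stands. A reader might infer that late events are excluded from assessment, and the text does not say that. But it does not say that the default is rebuttable or mere background either. Its verb tells the reader how an event will be treated, and a presumption by date is not an examination of evidence.

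Three stronger inferences are tempting and unsupported.

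- *The pause guidelines are weakened.* Guideline 7 concerns loss of the eye, which is not a listed condition and would be reached only indirectly. Guideline 2 spells out attribution through its own culture and participant-count criteria. Guideline 3 turns on normal progression of the eye condition, not on the 1-month sentence.
- *One masked reviewer receives both instructions for every late event.* An event arising more than 1 month after Treatment 1 but first noted within 14 days after Treatment 2 goes to the unmasked ophthalmologist.
- *The related-event rate shifts by a calculable amount.* Any such figure would need an assumed number of relabelled participants, which the documents do not give.

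**Conclusion.** The point holds as a minor inconsistency. Section 6.4 presumes an answer for late events of the listed types, 8.4 requires a judgement on each, and nothing ranks the two. If 6.4 is followed as written, the likely effect is a lean toward unrelated in the relatedness summaries, chiefly for non-serious ocular events.

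A reader might go further and conclude that the primary safety outcome is biased. The documents do not support that, because the outcome is incidence and severity, and neither depends on attribution. Serious events have further protection. Under 8.3 an event counts as serious if intervention is needed to prevent permanent vision loss. The Medical Monitor reviews all serious events and reports them to the DSMC (6.4, item 3). Where the Monitor and the investigator differ on causality, the Monitor's view prevails for regulatory reporting (8.4). That override does not extend to non-serious events or, on the text, to the relatedness tables.

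The size cannot be stated. The documents do not show how many late listed events occurred or how they were classified, and the number may be 0. The conclusion assumes only that some investigator could read the 6.4 sentence as an instruction, which its wording allows.

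**What to change.** Reconcile Protocol 6.4 with 8.4. The simplest way is to recast the two 1-month sentences as background. Suggested wording: *Side effects of the injection procedure are expected mainly within 1 month. Relationship to the cellular product and to study procedures is assessed for every adverse event under Section 8.4, whatever its timing.*

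Then check the adverse event records for listed conditions arising more than 1 month after a procedure. If any was classified by the presumption alone, re-assess it under 8.4 and flag the change in the adverse event listing. If none was, nothing further is needed.

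The cost is one or two sentences and a short record check. The downside is that a few more late events, in either arm, may be called possibly related. The displays by arm and by time since therapy will let readers weigh those.
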